7.4.1. HealthCore Integrated Research Environment

This PASS is a retrospective cohort study, using the HealthCore Integrated Research Environment, which includes automated health insurance claims from the HIRD augmented with information obtained from medical records and the NDI. This data source was chosen because of its very large size, its diverse geographical representation, and the high proportion of patients whose medical records were accessible. Medical record access was a key consideration as this will be necessary to accurately identify the primary endpoints of endometrial hyperplasia and endometrial cancer. The HIRD was chosen over other potential healthcare data sources because it provides both a large patient population and superior access to medical records. The HIRD has been previously used in pharmacoepidemiologic research.^{1,2,3,4} Additionally, data from the HIRD will be supplemented with review of full text medical records, which will be used to develop and validate algorithms for endometrial hyperplasia and endometrial cancer, as discussed in [Section 7.3.2](#).

The HIRD is a longitudinally integrated research database comprising payment claims for healthcare encounters among WellPoint, Inc.'s US health benefits insurance plans. WellPoint is one of the largest health benefit companies in terms of total patient enrollment in the US, with current enrollment of approximately 37.3 million members as of 30 June 2014. The HIRD contains approved and denied claims integrated across data sources and types (i.e., professional claims, facility claims, outpatient pharmacy claims, outpatient laboratory results, and enrollment information) as well as across years (from 2006 onwards). Data are obtained from affiliated health plans in the Northeastern, Mid-Atlantic, Southeastern, Midwest, Central, and Western regions of the US representing members in each of the 50 states of the US. The database represents claims from lines of business such as health maintenance organizations (HMOs), point of service (POS) plans, preferred provider organizations (PPOs), consumer directed health plans (CDHPs), and indemnity plans.

Specific data in the HIRD include enrollment data, medical care, prescription drug use, and health care utilization that can be tracked for each individual throughout the course of their enrollment in the selected health plans. Diagnoses and procedures for both outpatient and inpatient visits/stays are identified by ICD-9-CM diagnostic, ICD-9-CM procedure, CPT, and HCPCS codes. Outpatient pharmacy claims are captured by National Drug Codes (NDCs). Physician, specialist, and emergency room visits, as well as hospital stays, are captured in the database through ICD-9-CM diagnostic, ICD-9-CM procedure, CPT procedures, HCPCS, Uniform Billing Code of 1992 (UB-92) revenue (eg, room and board), and place of service codes. Information on physician specialty and laboratory result data are also retained in the database. The claims data in the HIRD also contain information necessary for economic analyses for both medical and pharmacy claims, including amounts charged to the provider and facility, amounts paid by the health plan and member (e.g., co-payments and deductibles), and coordination of benefits amounts.

7.5. Study Size

The focus of the sample size calculations is to determine the precision of the estimated HR that can potentially be achieved in the study depending on estimated patient accrual, event rates, and assumed true risk. Because of the CHMP’s concerns related to endometrial safety, endometrial hyperplasia and endometrial cancer are the primary endpoints and were used for these sample size calculations.

Precision is a measure inversely related to variance in estimation. For the HRs being estimated in this study, precision is represented by the width of two-sided 95% CI.

Duavee estimates are projections based on Pfizer commercial forecasts of product uptake only; no patient data are yet available. Projections are conservative and assume a reduction of 50% from the original US market forecasts. The estimated number of E+P HRT new users, their total person-time of follow-up, and the expected number of incident endometrial safety events observed in that cohort was obtained based on pilot analyses of the HIRD from the last three years. Therefore, the most recent 3 years of E+P HRT use in the HIRD is being used to project future E+P HRT uptake and use.

In the HIRD pilot analyses, the number of new users of E+P HRT products (i.e., patients with at least 12 months of continuous eligibility prior to the first use of E+P HRT) were identified using a one-, two-, and three-year time frame: 01 January 2011 – 31 December 2011, 01 January 2011 – 31 December 2012, and 01 January 2011 – 31 December 2013. The total person-time of follow-up accrued by the E+P HRT new users was calculated during these periods of interest together with the number of endometrial cancer and endometrial hyperplasia events occurring after the start of E+P HRT use.

All estimates (Table 1) were calculated with two-sided 95% CIs. According to the study plan, there will be a 4-year accrual period and patients will be followed for at least 1 year, with the first two cohorts being followed for a longer duration.

Table 1. Estimated 95% Confidence Intervals for Hazard Ratios of Endometrial Safety

Description	First Annual Report	Second Annual Report	Third Annual Report
Estimated numbers of new users of Duavee ^a	1,800	3,600	5,400
Estimated numbers of new users of E+P HRT ^b	36,651	44,122	50,350
Estimated person-years of follow-up for E+P HRT users ^b	27,768	58,399	89,438
Estimated endometrial cancer events after the start of E+P HRT use ^b	29	62	80
HRs (95% CI)			

Table 1. Estimated 95% Confidence Intervals for Hazard Ratios of Endometrial Safety

Description	First Annual Report	Second Annual Report	Third Annual Report
true HR=1.0	(0.18, 5.60)	(0.39, 2.56)	(0.48, 2.10)
true HR=1.5	(0.36, 6.33)	(0.68, 3.33)	(0.80, 2.83)
Estimated endometrial hyperplasia events after the start of E+P HRT use ^b	129	274	399
HRs (95% CI)			
true HR=1.0	(0.44, 2.26)	(0.64, 1.56)	(0.72, 1.39)
true HR=1.5	(0.76, 2.96)	(1.03, 2.19)	(1.13, 1.99)

a. *Duavee* estimates are projections based on Pfizer commercial forecasts of uptake only, no patient data are yet available. Person-time was calculated based on the assumption of 10 month treatment duration per patient⁹. Projections are conservative and assumed a reduction of 50% from actual US market forecasts.

b. E+P HRT users, person-time, and event estimates are derived from pilot analyses of the HIRD from the last three years of data.

Based on the projected numbers of patients initiating *Duavee* and E+P HRT as shown, for Year 1 of the US PASS, the estimated 95% CI of the HRs for the risk of endometrial hyperplasia in Table 1 imply that if the underlying (true) HR comparing *Duavee* users to E+P users is HR=1.0, then the point estimate of HR in the study will lie between 0.44 and 2.26, indicating that the study would be able to rule out the possibility that the true HR is greater than 2.26.

For Years 2 and 3, the estimated 95% CIs of the HRs for the risk of endometrial hyperplasia in Table 1 imply that if the underlying (true) HR comparing *Duavee* users to E+P users is HR=1.0, then the point estimates of HR in the study will lie between (0.64 and 1.56), and (0.72 and 1.39), respectively. This indicates that the study would be able to rule out the possibility that the true HR is greater than 1.56 at two years and 1.39 at three years.

These estimates are dependent on actual future E+P and *Duavee* drug uptake, the speed of patient accrual, safety event rates, and patient follow-up time; if these differ substantially from our estimates, then the precision of the HRs may change.

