7.2.2. Exclusion Criteria

Patients meeting any of the following criteria will be excluded from the study:

- Patients with an insufficient period of enrollment prior to their index prescription (e.g., 6 or 12 months as determined prior to the start of analysis) will be excluded. This period is necessary to determine if the patient is a new initiator of *Duavee* or E+P HRT without a history of unopposed estrogen use, and also to adequately ascertain baseline covariates/patient history;
- Patients without a uterus, i.e., males, or women for whom evidence of hysterectomy is identified prior to initiation of *Duavee* or comparator E+P HRT; and
- Patients with a history of any type of cancer in their baseline period.
- Patients for whom *Duavee*, comparator E+P HRT or unopposed estrogen are identified during the baseline period will be excluded from the main analyses. They will be evaluated in separate sub-analyses.

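### Table 1's E+P counts do not fit new initiation: the pilot states no drug-free baseline, so the comparator's size, person-years and events are probably overstated

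*Protocol*

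**What the plan says.** Section 7.5 takes the E+P cohort from a pilot in the HIRD. New users are described there as "patients with at least 12 months of continuous eligibility prior to the first use of E+P HRT", and they "were identified using a one-, two-, and three-year time frame"; all three windows open on 01 January 2011. Person-time and events were counted within those windows and carried forward as the study's projection. They fill the Table 1 rows "Estimated numbers of new users of E+P HRT", "Estimated person-years of follow-up for E+P HRT users", "Estimated endometrial cancer events after the start of E+P HRT use" and "Estimated endometrial hyperplasia events after the start of E+P HRT use".

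The study's own rule is stricter. Section 7.2.1 requires a baseline period with no Duavee or E+P. Section 7.2.2 says that women in whom Duavee, E+P or unopposed estrogen "are identified during the baseline period will be excluded from the main analyses". Under section 7.7.2, women with earlier E+P use contribute incidence rates only, not hazard ratios.

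**The concern.** Twelve months of eligibility shows that a woman was observable, not that she was untreated. If first use means the first fill after the window opens, a long-term user with a year of enrolment is counted as new at her next refill. The projection would then describe a population that the main analysis leaves out.

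The Table 1 intervals support the statements in the abstract and section 7.5 about which hazard ratios can be excluded. Section 7.1 says study duration was set from the sample size calculations, and section 7.9 cites the projected study size as a strength.

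**Working it through.** **Inputs (Table 1, reports 1 / 2 / 3)**
- E+P users: 36,651 / 44,122 / 50,350
- E+P person-years: 27,768 / 58,399 / 89,438
- Endometrial cancer events: 29 / 62 / 80
- Hyperplasia events: 129 / 274 / 399
- Duavee users: 1,800 / 3,600 / 5,400

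**Step 1: reproduce the stated intervals.** Treat the tabulated E+P events D as the total for both cohorts and split them by head count: e1 = D·HR·n1/(HR·n1 + n0), e0 = D − e1, limits = HR·exp(±1.96·√(1/e1 + 1/e0)). For first-report hyperplasia at HR = 1.0, e1 = 129 × 1,800/38,451 = 6.04 and e0 = 122.96. The standard error is 0.417 and the interval is 0.44 to 2.26, as stated. All 12 intervals in the table reproduce to within 0.01.

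**Step 2: entries per year.** 44,122 − 36,651 = 7,471 and 50,350 − 44,122 = 6,228. First-year entry is 36,651/7,471 = 4.9 to 36,651/6,228 = 5.9 times the later inflow.

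**Step 3: first-year follow-up.** 27,768/36,651 = 0.758 year per woman. Even entry over 12 months with nobody lost gives at most 0.50 year, or 36,651 × 0.5 = 18,326 person-years. Let a share f enter on day 1 and the rest evenly, with no loss: f × 1 + (1 − f) × 0.5 = 0.758, so f = 0.515. This is a floor. With no loss, the second year would add about 36,651 + 7,471/2 = 40,387 person-years, but it adds 58,399 − 27,768 = 30,631. Loss is therefore real, and any loss or later entry raises f.

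**Step 4: scenario for true initiators.** Assume 6,228 to 7,471 starters a year, even entry, no loss, and the pilot's event rates. Users after t years are t × annual starters, and person-years are t²/2 × annual starters. At t = 3 the event rates are 399/89,438 = 4.46 (hyperplasia) and 80/89,438 = 0.89 (cancer) per 1,000 person-years.

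| Third report | Table 1 | Scenario |
|---|---|---|
| E+P users | 50,350 | 18,684-22,413 |
| Person-years | 89,438 | 28,026-33,620 |
| Hyperplasia events | 399 | 125-150 |
| Endometrial cancer events | 80 | 25-30 |

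**Step 5: effect on the upper limits at HR = 1.0, reports 1 / 2 / 3.**

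| | Stated | Scenario, Table 1 formula |
|---|---|---|
| Hyperplasia | 2.26 / 1.56 / 1.39 | 3.3-3.4 / 1.8 / 1.5 |
| Endometrial cancer | 5.60 / 2.56 / 2.10 | 12-14 / 3.5-3.6 / 2.5-2.6 |

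This formula takes Duavee's events as a share of the E+P count, so shrinking the E+P cohort also cuts the implied Duavee events (first-report hyperplasia: 6.04 to 3.2-3.4). The 10-month treatment duration in Table 1 footnote a does not enter it.

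**Step 6: the same change with Duavee events added from 10 months of person-time per user.** First-report Duavee hyperplasia events are 1,800 × 10/12 × 129/27,768 = 6.97 with either E+P cohort. The hyperplasia upper limit moves from 2.14 to 2.4-2.5 in Year 1 and from 1.57 to 1.60 in Year 3. The starting values 2.14 and 1.57 belong to this alternative calculation and are not the protocol's figures.

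**The case against.** The protocol never says that ongoing users were counted. HIRD data run from 2006, so first use could mean first recorded use, and a parenthesis that omits a washout does not prove that none was applied. That stands: the point is an inference from the counts. Steady first-ever initiation, however, would produce neither the fall in entries nor a mean follow-up above 0.50 year, and the protocol explains neither.

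A reader might infer from the later increments that 80% of the first-year users were prevalent, since (36,651 − 7,471)/36,651 = 0.80. The documents do not support so exact a share. The windows are cumulative and count each woman once, so women restarting after a long gap are missed. The study's cancer, hysterectomy and unopposed-estrogen exclusions would lower the counts further. Only more than half is well supported.

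A reader might also infer that matching would fail. At 6,228-7,471 initiators against 1,800 Duavee users there are still about 3.5 to 4 comparators per Duavee user, and the ratio is the same at the third report.

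Finally, section 7.5 warns that precision may change if uptake, event rates or follow-up differ, and section 7.9 provides a Year 1 review of uptake. The first concerns uncertain future quantities and the second concerns Duavee. Neither covers a pilot definition that differs from the study's.

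**Conclusion.** The pilot's stated definition lacks the drug-free baseline that the main analysis requires. Table 1's figures imply that more than half of the first-year E+P users (at least 51.5%, with no loss) were already on treatment. The E+P users, person-years and events are therefore probably overstated for the new-user comparison. In the scenario, the third report has roughly 37% to 45% of the tabulated users (18,684/50,350 to 22,413/50,350).

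The exact size is not established. It rests on the later increments standing for annual initiation, even entry, no loss, and event rates from the pilot's mixed population carrying over to new users. The loss of precision depends on the formula: clear in all three reports under the one that reproduces Table 1, but mainly in Year 1 if Duavee events come from 10 months of person-time, because the Duavee arm then limits precision. The study aims at estimation, so no decision threshold fails. What is wrong is the projected comparator and the precision claimed from it.

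**What to change.** Rerun the pilot with the study's own exclusions: no E+P, Duavee or unopposed estrogen in baseline, and the cancer and hysterectomy exclusions of section 7.2.2. Use the baseline length finally chosen, since the protocol still leaves 6 or 12 months open. State the drug-free condition in section 7.5. Replace the E+P user, person-year and event rows of Table 1, recompute the intervals, and say how Duavee events enter them. Then restate the hazard ratios said to be excludable in the abstract and section 7.5. If a drug-free period was in fact applied, say so and explain the first-year excess and the 0.758-year mean follow-up.

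The cost is one rerun of an existing query, new table figures, and less favourable stated precision.

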Automated data from the HIRD will be linked to the US National Death Index (NDI) to ascertain mortality endpoints, including all-cause mortality and mortality specific to study endpoints of interest. Medical records (for a random sample of 400 potential cases) will be used to refine and validate algorithms for identification of the primary endpoints (endometrial hyperplasia and endometrial cancer). For development of the endometrial endpoint algorithms, clinical evidence available in the medical record, which includes all results of endometrial biopsies and clinician evaluations, will be considered the gold standard definition of case status against which the claims-based algorithm's performance will be measured.

Study size: Hazard ratios (HRs) and their 95% confidence intervals (CIs) expected to be observed in this study were estimated. Endometrial hyperplasia and endometrial cancer are defined as the primary endpoints and were used for these calculations. The number of *Duavee* users in HIRD during the study period has been projected based on Pfizer commercial forecasts only; no patient data are currently available. Estimates of E+P HRT use were obtained based on pilot analyses of the HIRD from the last three years. For Year 1 of the US PASS, the 95% CI of the HR for the risk of endometrial hyperplasia is projected to lie between 0.44 and 2.26 (assuming the true HR=1.0) indicating that the study would be able to rule out an HR greater than 2.26. For Years 2 and 3, the CIs for endometrial hyperplasia risk in the study is projected to lie between (0.64 and 1.56), and (0.72 and 1.39), respectively. This indicates that the study would be able to rule out an HR greater than 1.56 at two years and greater than 1.39 at three years.

Data analysis: Analyses will focus on the comparison between women initiating either *Duavee* or E+P HRT. Baseline characteristics will be compared across the two cohorts of new users to assess potential confounding variables. For each safety endpoint (venous thromboembolism [VTE], stroke, coronary heart disease [CHD], breast cancer, ovarian cancer, endometrial hyperplasia, and endometrial cancer, etc.), univariate and adjusted HRs will be estimated that compare incidence of the first occurrence of each safety event between *Duavee* and E+P HRT users.

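### Table 1's intervals reproduce only if the E+P-only event counts are taken as the total for both cohorts; alone this is a small, conservative error, to be corrected together with the exposure basis

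*Protocol*

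**What the plan says.** Protocol Section 7.5 projects the precision of the HR from four sets of inputs in Table 1, for the first, second and third annual reports:

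- Duavee users ("Estimated numbers of new users of" Duavee): 1,800 / 3,600 / 5,400, from a commercial forecast.
- "Estimated numbers of new users of E+P HRT": 36,651 / 44,122 / 50,350.
- "Estimated person-years of follow-up for E+P HRT users": 27,768 / 58,399 / 89,438.
- Events: 29 / 62 / 80 endometrial cancers and 129 / 274 / 399 hyperplasias. The hyperplasia row is labelled "Estimated endometrial hyperplasia events after the start of E+P HRT use", and the cancer row is worded the same way.

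The text says that the pilot counted person-time in E+P new users in 2011-2013, "together with the number of endometrial cancer and endometrial hyperplasia events occurring after the start of E+P HRT use". Duavee reached the US market in May 2014, and the section states that no Duavee patient data exist yet. Footnote a to Table 1 says Duavee person-time rests on 10 months of treatment per patient.

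On method, the section says only that "All estimates (Table 1) were calculated with two-sided 95% CIs". It gives no formula and no expected number of Duavee events. From the hyperplasia intervals at HR=1.0 it concludes that the planned cohort "would be able to rule out the possibility that the true HR is greater than 1.56 at two years and 1.39 at three years". The abstract repeats this ("greater than 1.56 at two years and greater than 1.39 at three years") and, like Section 7.5, gives 2.26 for Year 1.

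**The concern.** The variance of a log hazard ratio between two cohorts depends on the events in each. If the tabulated counts are E+P events, the Duavee events come on top of them. A formula that takes one total and divides it between the cohorts is valid only when it is given a total. Fed with a comparator-only count, it understates the events in both cohorts and makes the comparator's events fall as the assumed Duavee HR rises, which cannot happen.

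Table 1 is the protocol's only quantitative statement of precision. Section 7.1 bases the study duration on these calculations, and Section 7.9 plans a review of uptake after Year 1, with possible extension or further data sources. A recalculation that reused the formula would carry the error forward. The error grows with the Duavee share, and readers cannot see it because expected Duavee events are not shown.

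**Working it through.** Notation: nD and nE are the users in each cohort, E is the tabulated E+P event count, dD and dE are the events entering the variance, and limits are HR × exp(±1.96 × SE) with SE = sqrt(1/dD + 1/dE).

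**Step 1. Reproduce the printed table.** Take E as the total of both cohorts: p = HR·nD/(HR·nD + nE), dD = E·p, dE = E·(1−p).

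Hyperplasia, third report, HR=1.0: p = 5,400/55,750 = 0.0969; dD = 38.65; dE = 360.35; SE = 0.1693; limits (0.72, 1.39), as printed. At HR=1.5: p = 8,100/58,450 = 0.1386; dD = 55.29; dE = 343.71; limits (1.13, 1.99), as printed.

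Over both endpoints, both HRs and three reports, all 24 limits agree within 0.009. Twenty agree at two decimals; the other four are near misses such as 2.566 against 2.56.

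The implied E+P hyperplasia events are 360 at HR=1.0 and 344 at HR=1.5, while the row states 399.

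**Step 2. Try the alternatives.**

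- Duavee events added by head count: 0 of 24 limits agree at two decimals (3 within 0.01; largest difference 0.31).
- Duavee events added by footnote a's person-time: 0 of 24.
- Counts split by footnote a's person-time: 0 of 24.
- Duavee:E+P ratio left free: no additive ratio fits the four intervals of any report within 0.01. The split-total form fits every report, over ranges that include the tabulated user ratios 0.0491, 0.0816 and 0.1072.
- Hybrid with split-total Duavee events but the full E+P count: 19 of 24 limits, largest difference 0.022. This is close, but worse.

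**Step 3. Correct only the event total.** Keep head counts; dE = E and dD = HR·E·nD/nE. Hyperplasia, third report, HR=1.0: dD = 399 × 5,400/50,350 = 42.79; SE = 0.1609; limits (0.73, 1.37).

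**Step 4. Use footnote a's person-time as well.** Duavee person-years are 10/12 of the user numbers: 1,500 / 3,000 / 4,500. Then dD = HR·E·(Duavee person-years)/(E+P person-years). Hyperplasia, third report, HR=1.0: dD = 399 × 4,500/89,438 = 20.08; limits (0.64, 1.57).

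| Endpoint, HR | Report | Printed | Step 3: added, head count | Step 4: added, 10 months |
|---|---|---|---|---|
| Hyperplasia, 1.0 | 1 | 0.44, 2.26 | 0.45, 2.22 | 0.47, 2.14 |
| | 2 | 0.64, 1.56 | 0.65, 1.54 | 0.59, 1.71 |
| | 3 | 0.72, 1.39 | 0.73, 1.37 | 0.64, 1.57 |
| Hyperplasia, 1.5 | 1 | 0.76, 2.96 | 0.78, 2.90 | 0.80, 2.82 |
| | 2 | 1.03, 2.19 | 1.05, 2.15 | 0.96, 2.34 |
| | 3 | 1.13, 1.99 | 1.15, 1.95 | 1.04, 2.17 |
| Cancer, 1.0 | 1 | 0.18, 5.60 | 0.19, 5.38 | 0.20, 4.99 |
| | 2 | 0.39, 2.56 | 0.40, 2.48 | 0.32, 3.08 |
| | 3 | 0.48, 2.10 | 0.49, 2.02 | 0.37, 2.72 |
| Cancer, 1.5 | 1 | 0.36, 6.33 | 0.37, 6.02 | 0.40, 5.67 |
| | 2 | 0.68, 3.33 | 0.71, 3.19 | 0.59, 3.80 |
| | 3 | 0.80, 2.83 | 0.83, 2.70 | 0.66, 3.43 |

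**Step 5. Why Steps 3 and 4 differ.** A head-count split gives Duavee users the same mean follow-up as E+P users: 27,768/36,651 = 0.758, 58,399/44,122 = 1.324 and 89,438/50,350 = 1.776 years. Footnote a gives 10/12 = 0.833 years throughout. Hence Step 4 is narrower than Step 3 in the first report and wider in the second and third.

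**The case against.** The formula is inferred, since the protocol prints none. A figure such as 344 E+P events is a reconstruction, and the hybrid in Step 2 is not far behind. That stands as a limit on certainty. But the split-total form fits best at the tabulated user numbers, and every additive form fails, so the printed limits do not follow from the inputs as labelled.

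The effect is also small. The three quoted exclusion limits move by under 2%, the largest shift is about 5%, and that occurs where only about 2 Duavee events are expected. The Duavee numbers are a halved commercial forecast, the section warns that precision depends on uptake and follow-up, and Section 7.7.7 says the aim is estimation. All of this stands, and it keeps the point modest.

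A reader might infer that Table 1 overstates the study's precision because of the wrong total. The documents do not support that: this error alone makes the intervals slightly too wide. Nor do they support the opposite inference, that correcting it secures upper limits of 1.54 and 1.37. Those figures keep the head-count basis, which differs from footnote a.

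**Conclusion.** The printed intervals treat E+P-only event counts as the two-cohort total, and this contradicts the row labels and the description of the pilot. With head counts kept, all 12 intervals change at two decimals, upper limits are about 1-5% too high, and none changes sides of 1. Expected Duavee events are understated by about 5-10% at HR=1.0 and 7-14% at HR=1.5.

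The larger uncertainty is exposure. With footnote a's 10 months, the second- and third-report hyperplasia upper limits at HR=1.0 are 1.71 and 1.57 against the printed 1.56 and 1.39, and the second-report lower limit at HR=1.5 falls from 1.03 to 0.96. Footnote a refers to treatment duration, whereas Sections 7.1 and 7.4 keep women at risk after discontinuation, so the intended Duavee person-time is itself unsettled. Correcting the total without settling it would move the second- and third-report limits further from the result on footnote a's basis.

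The calculations assume the tabulated inputs, 1.96 for the 95% level, and the usual variance 1/dD + 1/dE.

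**What to change.** Recompute Table 1 once, with SE = sqrt(1/dE + 1/dD). Here dE is the stated E+P count, and dD = HR × E+P events per person-year × Duavee person-years, added to dE. State the formula and the Duavee person-time used, reconcile that person-time with footnote a and with the at-risk definition in Sections 7.1 and 7.4, and add a row with dD. Then restate the exclusion limits in Section 7.5 and the abstract. The cost is one recalculation and edits in two places; neither design nor data collection changes.

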7. RESEARCH METHODS

7.1. Study Design

This PASS is a retrospective cohort study utilizing a healthcare claims data source (HIRD) in the US. Two (2) treatment groups (*Duavee* and E+P HRT) will be identified, followed, and reported upon using annual database updates. A new-user cohort design will be used for the main analysis and users with a history of (E+ P) HRT will be examined in sub-analyses. The study will accumulate data for 4 years (May, 2014-May, 2018) as it follows a dynamic cohort of patients that enter the study at different times, based on when *Duavee* or E+P HRT is initiated.

Figure 1 shows the length of study follow-up according to when new users enter the cohort.

The study duration was determined based on sample size calculations, and is the soonest that clinically meaningful HRs for endometrial hyperplasia and endometrial cancer can be detected. Study years and reporting intervals will run from May 1 through April 30 of the next year. Interim (follow-up) and final reports will contain both interval and cumulative data.

All patients in the HIRD who initiate *Duavee* or E+P HRT in the study period (2014-2018) will be considered for inclusion. This PASS is a retrospective cohort study using secondary data. The source data has been accruing since *Duavee* became available in the US in May, 2014. In accordance with EMA Pharmacovigilance Guidance (Module VIII)⁵, the start of a PASS using secondary data is defined to be when the analytic dataset is extracted. This will not be done for this PASS until the study protocol has been approved by the PRAC.

Follow-up will continue from the first use of *Duavee* or E+P HRT through to the earliest of the following censoring events:

- End of continuous health plan eligibility;
- Switch from *Duavee* to an E+P HRT medication or vice-versa;
- (Note: Any use of an estrogen or estrogen-containing product (Appendix 2) that differs from the HRT treatment regimen dispensed on the index date will censor follow-up. This does not include dispensing of a topical estrogen that is a single-unit

E+P HRT. As described in [Section 7.7.4](#), sensitivity analyses exploring the impact of this criterion will be performed.

- First occurrence of a safety endpoint.

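### Table 1's intervals do not follow from the 10-month Duavee person-time in its footnote, and the "rule out" bounds taken from them are met only about half the time

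*Protocol*

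**What the plan says.** Protocol section 7.5 projects precision from Table 1. The Duavee row gives "1,800 3,600 5,400" new users at the three annual reports. The E+P rows give 36,651/44,122/50,350 new users, 27,768/58,399/89,438 person-years, 29/62/80 endometrial cancer events and 129/274/399 hyperplasia events, the events being labelled as occurring after the start of E+P use. For Duavee, footnote a states: "Person-time was calculated based on the assumption of 10 month treatment duration per patient". No Duavee person-years are printed.

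For hyperplasia with a true HR of 1.0 the intervals are (0.44, 2.26), (0.64, 1.56) and (0.72, 1.39). Section 7.5 concludes that a study of this size "would be able to rule out the possibility that the true HR is greater than 1.56 at two years and 1.39 at three years". The Abstract repeats that it "would be able to rule out an HR greater than 1.56 at two years and greater than 1.39 at three years". Both also give 2.26 for Year 1.

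Section 7.5 adds that "patients will be followed for at least 1 year, with the first two cohorts being followed for a longer duration". Section 7.1 rests the study duration on these calculations. Sections 7.1 and 7.4 keep patients at risk after treatment is discontinued.

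**The concern.** The footnote is the only statement of how Duavee person-time entered the table. If it were followed, the Duavee arm would contribute far fewer events in Years 2 and 3 than the printed intervals need, so a reader cannot tell which figure to trust. The rule-out sentences then read an upper limit, computed for an estimate of exactly 1.0, as something the design delivers. These figures go to the regulator and underlie the choice of duration. Section 7.9 plans a review of uptake after Year 1, with possible extension of the study or added data sources, and that decision needs sound precision figures.

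**Working it through.** **Inputs.** All come from Table 1 and footnote a. The table uses two-sided 95% intervals, so z = 1.96. The formula is CI = HR × exp(±1.96 × SE), with SE = √(1/d + 1/E), where d is expected Duavee events and E is E+P events.

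**Step 1: reproducing the printed table.** Take the printed event count D as the total for both arms and split it by head-count. The Duavee share is s = HR×N_D/(HR×N_D + N_E), where N_D and N_E are the Duavee and E+P user counts.
- Year 3 hyperplasia, HR=1.0: s = 5,400/(5,400 + 50,350) = 0.0969. Duavee events are 399 × 0.0969 = 38.6, leaving 360.4 for E+P. SE = √(1/38.6 + 1/360.4) = 0.169, giving (0.72, 1.39) as printed.
- Year 1 gives upper limits of 2.26 for hyperplasia and 5.60 for cancer, both as printed.
- Across all rows, 20 of 24 limits match exactly and the other four are within 0.01.

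A head-count split gives Duavee users the mean follow-up of E+P users (0.76/1.32/1.78 years), which is 1,364/4,765/9,592 person-years. The 10-month figure plays no part.

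**Step 2: following the footnote.** Duavee person-years are users × 10/12 = 1,500/3,000/4,500. The E+P hyperplasia rates are 129/27,768, 274/58,399 and 399/89,438, i.e. 4.65/4.69/4.46 per 1,000 person-years. Expected Duavee events are therefore 7.0/14.1/20.1.

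| Hyperplasia, HR=1.0 | Year 1 | Year 2 | Year 3 |
|---|---|---|---|
| SE, 10 months | 0.389 | 0.273 | 0.229 |
| CI, 10 months | (0.47, 2.14) | (0.59, 1.71) | (0.64, 1.57) |
| CI, printed | (0.44, 2.26) | (0.64, 1.56) | (0.72, 1.39) |

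At HR=1.5 in Year 2 the expected Duavee events are 21.1 and the lower limit is 0.96; the table prints 1.03. Endometrial cancer in Year 3 at HR=1.0 becomes (0.37, 2.72); the table prints (0.48, 2.10). None of the 24 printed limits is matched with 10-month person-time under the normal-approximation formulas tried.

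**Step 3: back-solving the printed limits.** SE = ln(U/L)/3.92, d = 1/(SE² − 1/E), and person-years = d divided by the E+P rate. For hyperplasia at HR=1.0:
- Year 1: SE 0.417, d = 6.0, about 1,290 person-years (0.86 of the footnote).
- Year 2: SE 0.227, d = 20.8, about 4,440 (1.48 times).
- Year 3: SE 0.168, d = 39.0, about 8,740 (1.94 times).

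Rounding of the printed limits allows 4,320–4,560 in Year 2 and 8,440–9,050 in Year 3, so it does not explain the gap. The cancer rows agree (0.87/1.47/1.92).

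**Step 4: the rule-out statement.** With a true HR of 1.0, the chance that the study's upper limit falls below a bound B is Φ(ln B/SE − 1.96). With the printed SE, ln B/SE is about 1.96 by construction, so the chance is Φ(0) = 50% in each year. With 10-month person-time it is about 37% for 1.56 and 30% for 1.39.

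The HR excluded with 80% probability is exp((1.96 + 0.84) × SE):

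| | Year 1 | Year 2 | Year 3 |
|---|---|---|---|
| Stated bound | 2.26 | 1.56 | 1.39 |
| 80%, printed SE | 3.22 | 1.89 | 1.60 |
| 80%, 10 months | 2.97 | 2.15 | 1.90 |

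**Step 5: minimum follow-up.** Accrual runs four years from May 2014. Section 4 ends data collection on 01 May 2018, and section 7.1 censors at the end of the study period. A woman who starts treatment after May 2017 cannot reach one year of follow-up.

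**The case against.** The strongest reply is that 10 months is a treatment duration, while the main analysis counts time at risk beyond discontinuation, so Duavee follow-up may well exceed 10 months per user by Year 3. This stands. The intervals in step 2 are therefore conditional on the footnote and are not replacements for the table. As an illustration under an assumption the protocol does not make (even accrual of 1,800 users a year, no dropout), the ceiling would be 900/3,600/8,100 person-years. On that assumption neither the footnote's 1,500 in Year 1 nor the printed intervals' implied totals could be reached.

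A reader might infer that the Duavee row is annual and was summed again, to 10,800 users and 9,000 person-years. The documents do not support this. That reading gives a Year 3 cancer upper limit of 2.06 at HR=1.0 and 2.75 at HR=1.5, against 2.10 and 2.83 printed. Section 7.3.3, with its 3,600-user threshold expected around the Final Report, also fits a cumulative row.

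On the rule-out wording, section 7.5 presents the calculation as precision, and section 7.7.7 says the aim is estimation rather than testing. That is fair, and an 80% figure is one choice among several. It does not rescue the sentence, because no probability is attached to it. The section 7.5 caveat covers changed inputs, not this inference.

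**Conclusion.** Wrong as written, and worth correcting. The footnote and the printed intervals cannot both describe one calculation: they differ by a factor of about 1.5 in Year 2 and 1.9 in Year 3, and by 0.86 in Year 1. The likeliest account, inferred from the fit alone, is that the 10-month person-time was never used and that events labelled as E+P events were shared between the arms. The documents do not settle whether the footnote or the intervals should give way. The back-solved person-years assume the normal approximation and Table 1's E+P rates.

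The rule-out fault does not depend on that question: the stated bounds hold about half the time when the true HR is 1.0, even with the printed intervals. The one-year minimum contradicts the protocol's own dates, but it is a separate slip and alters no figure in Table 1.

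One might go further and say that the claims of detectable or excludable risks in sections 7.1 and 7.9 must be withdrawn, in particular that the duration "is the soonest that clinically meaningful HRs for endometrial hyperplasia and endometrial cancer can be detected". The documents do not support that step. Table 1 has no fourth-year column, the protocol names no HR as clinically meaningful, the wide cancer intervals are printed openly, and section 7.9 admits limited precision and long cancer latency.

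**What to change.** - State the projected Duavee at-risk person-years for each report, consistent with the follow-up rule in sections 7.1 and 7.4.
- Count E+P events as E+P events only, and derive expected Duavee events from the Duavee person-years.
- Recompute every interval in Table 1, and bring footnote a, section 7.5 and the Abstract into line.
- Reword the rule-out sentences as the upper limit expected if the estimate equals 1.0, or give the HR excluded with a stated probability such as 80%.
- Replace the one-year minimum with the follow-up that the dates allow.

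The cost is a recalculation and changes of wording. No endpoint, cohort or analysis changes. The stated precision may become less favourable, depending on the person-years that can be justified.
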